## 7.2.1. Dose Modifications: Dose Titration, Dose Reduction and Dose Delay

### 7.2.1.1. Dose Titration

Subjects may be dose-titrated to 1.25 mg/kg, but the maximum total dose should not exceed 120 mg, during the treatment period as well as during the Long-term Treatment Period and Open-label Phase, as long as a dose delay or reduction is not required (see Section [7.2.1.2](#)). The dose titration criteria are defined as follows:

- Transfusion reduction over at least two dose cycles (~6 weeks) is < 33%, compared to the transfusion burden (units/wk) at baseline, or
- Transfusion reduction over at least two dose cycles (~6 weeks) is  $\geq 33$  but  $\leq 50\%$  compared to baseline, at the discretion of the Investigator.

After safety and efficacy data review, the sponsor may allow dose titration following special requests, such as, but not limited to, subjects who have been dose reduced once, but lost the response to treatment.

Starting dose with dose titration and reductions are presented below for reference (Table 4).

**Table 4: Starting Dose Level with Dose Reductions and Dose Titration**

3 rd Dose Reduction (~ 25 %)	2 nd Dose Reduction (~ 25 %)	1 st Dose Reduction (~ 25 %)	Starting Dose Level	1 st Dose Titration
0.45 mg/kg	0.6 mg/kg	0.8 mg/kg	1.0 mg/kg	1.25 mg/kg

#### 7.2.1.2. Dose Delay and Dose Reduction

Dose delay of luspatercept from the planned dosing schedule may occur due to increased hemoglobin or adverse events. Table 5 provides guidelines for dose modifications and dose delay.

Subjects can experience a dose reduction based on the change in mean Hb level (Hb not influenced by a transfusion) with respect to the last dose, as well as related adverse events, as detailed in Table 5. Hemoglobin not influenced by a transfusion should be considered for dosing, delays and discontinuation actions related to luspatercept. Hemoglobin not influenced by a transfusion is considered a Hb within 14 days post-transfusion. If a subject is experiencing a dose delay due to Hb increase, Hb measurement should occur every week.

If dose delay is 15 weeks or longer from the previous dose administered, including cases of elective surgery/hospitalization, the treatment should be discontinued. Dose delay for AE unrelated to the study drug, as per discretion of the Investigator are allowed. Assessments to be performed during the dose delay period are detailed in Section 6.

Celgene or its authorized representative should be notified of dose modification or interruption within 24 hours.

Dose reduction and dose delays guidelines are detailed in Table 5.

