#### 1.2.1.4. Potential Risks of Human Use

Increases in hematologic parameters (RBC, hemoglobin, hematocrit, reticulocytes) are expected pharmacologic effects of luspatercept treatment. Increases in systolic and diastolic blood pressures may occur in concert with increases in hemoglobin values. Excessive or rapid increases in hemoglobin or blood pressure may occur and will be monitored. Dose modifications rules for individual subjects and dose titration/reduction rules will be utilized to minimize risks associated with increased RBC parameters.

Adverse events considered probably or possibly related to study drug that were reported in the Phase 1 study in healthy volunteers included injection site hemorrhage and injection site macule. As of 07 July 2016, adverse events reported regardless of causality in the ongoing Phase 2 studies in MDS and  $\beta$ -thalassemia included bone pain, headache, asthenia, myalgia, arthralgia, nasopharyngitis, pyrexia, oropharyngeal pain, diarrhea, fatigue, musculoskeletal pain, cough and influenza. CCI [REDACTED]

CCI [REDACTED] Luspatercept must not be given to a pregnant woman or a woman who intends to become pregnant. If a woman becomes pregnant while taking luspatercept, the medication must be stopped immediately.

If luspatercept is taken during pregnancy, a teratogenic effect in humans cannot be ruled out. In addition, since it is unknown if luspatercept is excreted in breast milk, breastfeeding is prohibited in all protocols.

CCI [REDACTED]

As with all biologics, there is the potential for antidrug antibodies (ADA) that can be associated with increased drug clearance and hypersensitivity reactions. CCI [REDACTED]

Please refer to the Investigator's Brochure (IB) for additional information regarding findings from toxicology studies. CCI [REDACTED]

[REDACTED] Safety will be monitored closely through adverse event (AE) reporting, clinical laboratory tests, vital signs, and physical examinations, and ongoing review of unblinded data by an external DMC.

A comprehensive review of luspatercept, as well as details regarding the information summarized above, is provided in the IB. The most recent version of the luspatercept IB should be reviewed prior to initiating the study.

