##### Subjects initially assigned to placebo:

- can enter the Open-label Phase only if the DMC allows it, as outlined above.
- can enter the Open-label Phase even if they have discontinued the double-blind phase, but were compliant with the protocol 48 weeks post Dose 1 Day 1, and continue their participation in the Post-treatment Follow-up Period until the time of unblinding. can stay in the Open-label Phase until all subjects initially assigned to luspatercept complete the total treatment duration of 5 years from subjects' Dose 1 Day 1 in the treatment period of this ACE-536-B-THAL-001 study or discontinue earlier.
- at the time of unblinding, placebo subjects who discontinued treatment and continued their participation in the Post-treatment Follow-up Period until the time of unblinding

will have the opportunity to enter the Open-label Phase, if they still fulfill the following main eligibility criteria, prior to receiving their first dose of luspatercept:

- Inclusion criteria: numbers 6 and 8 (Refer to Section 4.2);
- Exclusion criteria: numbers “1-10, 15-17 and 21” (Refer to Section 4.3)

Per Investigator’s request, subjects who discontinue luspatercept in the double-blind Treatment Period for reasons not related to subject’s safety, and are still in the Post-treatment Follow-up Period at the time of unblinding, may access the Open-label Phase and be re-treated with luspatercept after consultation with Sponsor Medical Monitor and review of safety and efficacy data as long as they still fulfill the above eligibility criteria prior to Dose 1 Day 1.

**Note:** Subjects who discontinue from the study before the unblinding and without completing the PTFP period are not allowed to re-enter this study and access luspatercept in the Open-label Phase.

Subjects will be discontinued from study as appropriate, for reasons listed in Section 11.

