### 7.2. Treatment Administration and Schedule

Luspatercept or placebo will be administered as a subcutaneous (SC) injection to subjects by the study staff at the clinical site and administration will be documented in the subject's source record. Subcutaneous injections will be given in the upper arm, thigh, and/or abdomen. Calculated doses requiring reconstituted volume greater than 1.2 mL should be divided into separate similar volume injections across two separate sites using the same anatomical location but on opposite sides of the body (example left thigh and right thigh). The maximum volume per SC injection should not exceed 1.2 mL. The maximum total dose per administration should not exceed 120 mg, which results in 2.4 mL maximum total volume after reconstitution. The injection sites can be rotated according to Investigator judgment, and the injections can be given in the following order as needed, for example: 1) right upper arm, 2) left upper arm, 3) right upper thigh, 4) left upper thigh.

Subjects will be assigned to treatment as per one of the following regimens:

- Luspatercept starting dose level 1 mg/kg SC once every 21 days
- Placebo SC once every 21 days

The investigational product should be administered according to the following criteria:

- **Pre-treatment/ pre-transfusion** Hb value is  $< 11.5$  g/dL and increase of Hb  $\leq 2.0$  g/dL compared to the pre-dose Hb of Day 1 of the previous treatment dose cycle, and
- Any related adverse events must be  $< \text{Grade } 2$  according to NCI CTCAE criteria ([Appendix C](#))
- WBC  $< 3 \times$  baseline. Corrected WBC values should be used to establish the baseline WBC. Baseline is equal to the highest WBC value between Screening WBC and Study Dose 1 Day 1.
- Leukopenia, neutropenia and/or thrombocytopenia should be  $< \text{Grade } 3$ , as per NCI CTCAE criteria ([Appendix C](#))
- $< 50 \%$  increase from baseline in transfusion burden in combination with shift from baseline (worsening) of  $< 2$  grades in leukopenia, neutropenia or thrombocytopenia

Please refer to [Table 5](#) for guidelines on dose modifications and dose delays.

Subjects must have Hb assessed and results available prior to each study drug administration. If a transfusion occurred prior to dosing, the pre-transfusion Hb should be considered for dosing purposes (ie, Hb  $\geq 14$  days post- transfusion).

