**Table 5: Dose Delay, Dose Reduction and Discontinuation Guidelines: (Continued)**

Event at the Day of Dosing	Action
> 2 dose reductions due to related AE a	Discontinue treatment
Increase in Hb >2.0 g/dL compared to pre-dose Hb of Day 1 of the previous treatment dose cycle b	Reduce dose by 25% d if ΔHb not influenced by RBC transfusions
Hb ≥ 11.5 g/dL b	Dose delay until Hb ≤ 11.0 g/dL
Worsening of Anemia	

A ≥ 50 % increase from baseline in transfusion burden in combination with an unexplained shift from baseline (worsening) of ≥ 2 gradesi in leukopenia, neutropenia or thrombocytopeniah.
	
Dose delayc and repeat WBC, neutrophils and platelets weekly for two consecutive weeks.
 
 
• If WBC, neutrophils and platelets are resolved to ≤ Grade 1 or baseline, continue with dosing at the same dose level.
 
• If WBC, neutrophils and platelets are Grade 2 and above baseline, then continue with dose delay until resolution to ≤ Grade 1 and evaluate for alternative explanations of cytopenia as per standard clinical practice.
 
• If shift (worsening) of ≥ 2 grades is maintained for ≥ 14 days or thrombocytopenia does not improve to < Grade 2 within 14 days and no alternative explanation is identified, then perform bone marrow assessment.                         
 
○ If hematologic malignancy is confirmed, discontinue treatmentg
 
○ If hematologic malignancy is not confirmed, then discuss future dosing with medical monitor.
 
 
 

WBC	

WBC counte ≥2X baseline in the absence of an associated condition (eg, infection or concomitant corticosteroid use)
	
Continue treatment, repeat WBC within 1 week
 
 
• If repeat WBC remains ≥ 2 X above baseline Investigator should assess the cause of increase to exclude hematologic malignancy as per standard clinical practice.
 
• If hematologic malignancy is confirmed, discontinue treatment.g
 

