**Table 5: Dose Delay, Dose Reduction and Discontinuation Guidelines: (Continued)**

Event at the Day of Dosing	Action

Grade <math>\geq</math> 3 Leukopenia, neutropenia and/or thrombocytopeniai
	
Dose delayc and, repeat assessment weekly for two consecutive weeks
 
 
• Investigator should assess the cause of cytopenia per standard clinical practice to exclude hematologic malignancy.
 
• If WBC, neutrophils and platelets resolved to <math>\leq</math> Grade 1, continue with dosing at the same dose level.
 
• If WBC, neutrophils and platelets <math>\geq</math> Grade 2 and above baseline sustained for <math>\geq</math> 14 days perform bone marrow assessment. 
 
○ If hematologic malignancy is confirmed, discontinue treatmentg
 
○ If hematological malignancy is not confirmed, then discuss future dosing with a medical monitor.
 
 
 

Grade 3 Leukocytosisf
	
Discontinue treatment

a Possibly, probably or definitely related.

b Based on the **pre-treatment** Hb value not influenced by transfusion (ie,  $\geq$  14 days post- transfusion); Hb should be rechecked weekly during dose delay.

c If dose delay is 15 weeks or longer from the prior dose administration, treatment should be discontinued.

d Refer to [Table 4](#) for dose reductions.

e Central laboratory corrected WBC values must be used for confirming the Investigator decision, which may be based on the local lab result. The baseline WBC is defined as highest WBC value between Screening WBC and Study Dose 1 Day 1.

f Grade 3 Leukocytosis (as per CTCAE, ie, WBC above 100K) should be based on Central Laboratory values, as applicable.

g For full list of events triggering discontinuation, see Section 11 of the protocol.

h For reference, as per CTCAE : Grade 1 Leukopenia :  $<$  LLN – 3000/mm^3; Grade 1 Neutropenia :  $<$  LLN – 1500/mm^3; Grade 1 Thrombocytopenia :  $<$  LLN – 75'000/mm^3; Grade 2 Leukopenia :  $<$  3000 – 2000 / mm^3; Grade 2 Neutropenia :  $<$  1500 – 1000 / mm^3; Grade 2 Thrombocytopenia :  $<$  75'000 – 50'000 / mm^3.

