10.5.11 Pre-transfusion Hemoglobin Change from Baseline

To estimate the change of pre-transfusion hemoglobin value after dosing within each 12-week interval (week 1-12, week 13-24, week 25-36, week 37-48, week 49-60, etc.), summary statistics for the baseline, post-baseline and change from baseline pre-transfusion hemoglobin values will be provided by treatment group. The number and percentage of subjects meeting selected change category (Decrease ≥ 2 g/dL, Decrease ≥ 1.5 -<2 g/dL, Decrease ≥ 1 -<1.5 g/dL, Decrease ≥ 0.5 -<1 g/dL, Decrease >0 -<0.5 g/dL, Increase ≥ 0 -<0.5 g/dL, Increase ≥ 0.5 -<1 g/dL, Increase ≥ 1 -<1.5 g/dL, Increase ≥ 1.5 -<2 g/dL and Increase ≥ 2 g/dL) will be provided separately. Baseline pre-transfusion hemoglobin is defined as mean of all documented pre-transfusion hemoglobin values collected during the 24 weeks prior to Dose 1 Day 1. Post-baseline pre-transfusion hemoglobin is

defined as mean of all documented pre-transfusion hemoglobin values collected during each 12-week interval. The same summary statistics and categorized pre-transfusion hemoglobin change from baseline analyses will be repeated for erythroid responders (33% and 50% at week 13-24), non-responders (33% and 50% at week 13-24), and responders (33% and 50% during any 12-week interval) respectively. A similar analysis will be conducted for each 24-week interval.

In addition, hemoglobin values from central lab will be summarized in the same way by 12-week interval. Only hemoglobin measurements on the same day as transfusion or 14 days after transfusion date will be included, i.e., if a hemoglobin measurement occurs within 14 days after any transfusion, the hemoglobin value will be excluded from analysis.

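### Protocol Section 7.2.1.2 states the 14-day rule for transfusion-free haemoglobin backwards; a separate minor gap leaves the contraception criterion out of one open-label re-entry check

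*Protocol*

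**What the plan says.** **The Hb rule.** Protocol Section 7.2.1.2 tells sites to base dosing, delay and discontinuation on Hb that a transfusion has not affected. It then defines that value: "Hemoglobin not influenced by a transfusion is considered a Hb within 14 days post-transfusion". This is current protocol text, not part of an amendment summary.

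The same rule appears elsewhere in the protocol with the opposite direction:

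- Table 5, footnote b, attached to both Hb rows: "Hb value not influenced by transfusion (ie, $\geq$ 14 days post- transfusion".
- Section 7.2, and in near-identical words Section 6: "the pre-transfusion Hb should be considered for dosing purposes (ie, Hb $\geq 14$ days post- transfusion".

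Two Table 5 rows depend on the definition. Hb at or above 11.5 g/dL leads to a delay until Hb is 11.0 g/dL or lower. A rise above 2.0 g/dL from the pre-dose value of the previous cycle leads to a 25% reduction, but only "if ΔHb not influenced by RBC transfusions". Section 7.2.1.2 itself refers to Table 5 three times, ending with "Dose reduction and dose delays guidelines are detailed in Table 5".

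SAP Section 10.5.11, on summaries of central-laboratory Hb, says: "if a hemoglobin measurement occurs within 14 days after any transfusion, the hemoglobin value will be excluded from analysis".

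**Open-label re-entry.** Section 3.1.4 gives the list for placebo subjects who had stopped treatment as "Inclusion criteria: numbers 6 and 8", plus a set of exclusions. It applies the same list to luspatercept discontinuers re-treated at the investigator's request. Section 6.4 lists inclusion criteria 6 and 7 with the same exclusions, and restricts the check to placebo subjects. Criterion 7 covers pregnancy testing and contraception for women of childbearing potential; criterion 8 is the male contraception criterion.

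**The concern.** The days just after a transfusion are when Hb is most affected by it, so the Section 7.2.1.2 sentence contradicts its own purpose as well as the rest of the protocol. It sits in the section that governs dose delay and reduction. Sections 6.2.1, 6.3.1 and 6.4.1 send sites there, together with Table 5, when a dose is delayed for raised Hb.

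The Hb rules are a safety measure. Section 1.2.1.4 says: "Dose modifications rules for individual subjects and dose titration/reduction rules will be utilized to minimize risks associated with increased RBC parameters". A site applying the sentence as written could hold or reduce a dose because of transfused cells and not because of the drug.

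The re-entry point is a different and smaller matter. A woman who stopped luspatercept and is later re-treated open-label meets no listed step at which she confirms the contraception commitment again. Section 1.2.1.4 says that a teratogenic effect cannot be ruled out.

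**Working it through.** No arithmetic applies to the Hb rule. The check is to set the statements side by side and follow a high value through them.

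| Place | Time since transfusion for a usable Hb | What it governs |
|---|---|---|
| Protocol 7.2.1.2 | within 14 days | dosing, delay, discontinuation |
| Protocol 6 | 14 days or more | Hb used for dosing |
| Protocol 7.2 | 14 days or more | Hb used for dosing |
| Protocol Table 5, footnote b | 14 days or more | both Hb rows |
| SAP 10.5.11 | values within 14 days are dropped | descriptive Hb summaries |

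In the protocol, one statement stands against three. The two definitions can share at most day 14 itself, so no reading reconciles them. The SAP rule agrees with the three but is an analysis rule (it also keeps Hb taken on the day of a transfusion), so it is supporting context and not a further dosing instruction.

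**Case A: Hb taken less than 14 days after a transfusion, high because of the transfused cells.**
- Section 7.2.1.2 read literally: the value counts. At 11.5 g/dL or above it triggers a delay until 11.0 g/dL or lower. A rise above 2.0 g/dL triggers a reduction, for a first step 1.0 to 0.8 mg/kg in Table 4.
- Footnote b and Section 7.2: the value does not count. The pre-transfusion Hb decides, and the dose may be given at the same level.
- Result: the texts conflict, and the literal reading produces an unneeded action.

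**Case B: Hb taken more than 14 days after a transfusion, high because of the drug.**
- Section 7.2.1.2 read literally: the value does not qualify.
- Section 7.2 separately allows dosing only if the pre-treatment or pre-transfusion Hb is below 11.5 g/dL and the rise is no more than 2.0 g/dL. That criterion does not use the Section 7.2.1.2 definition. Footnote b also counts the value.
- Result: two independent rules still lead to action.

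**How often the window matters.** Section 1.3.1 gives usual transfusion intervals of two to four weeks, inclusion criterion 5 allows no transfusion-free gap above 35 days, and dosing is every 21 days. A dosing-day Hb can therefore readily fall within 14 days of a transfusion. The documents give no basis for a count of affected decisions.

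**Re-entry lists.** The inclusion criteria that apply to each group are:

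- Placebo discontinuers: {6, 8} from Section 3.1.4 together with {6, 7} from Section 6.4 gives {6, 7, 8}; none missing.
- Luspatercept discontinuers re-treated: {6, 8} from Section 3.1.4 only; criterion 7 is missing, which concerns women only.

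Table 3, footnote 18, also describes the open-label eligibility column in terms of placebo subjects.

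**The case against.** The strongest reply is that this is a slip of wording with little practical effect, and much of that stands. Both Hb rows in Table 5 carry the correct footnote. Section 7.2.1.2 defers to Table 5, and the Amendment 1 rationale (item 1.5.6) names Table 5 as the place where transfusion influence is defined. Dose reductions are registered through the interactive response system, and dose modifications are to be notified to the sponsor within 24 hours.

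A reader might infer from the reversed sentence that a genuine drug-driven Hb rise would go unanswered. The documents do not support that. The Section 7.2 dosing criteria stand on their own and would withhold the dose whatever Section 7.2.1.2 says, and footnote b counts the value.

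On re-entry, a reader might infer that re-treated women are under no contraception duty. That also goes too far. Criterion 7 binds participating women during study therapy, including interruptions, and for 12 weeks afterwards. Exclusion 15 (pregnant or lactating) is re-checked, a pregnancy test is required at each open-label dose, Section 10.4.1 advises against pregnancy throughout the study, and the medical monitor must be consulted. Table 3, footnote 18, also refers the reader back to Section 3.1.4. The group is an exception, limited to discontinuations unrelated to safety.

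What survives is narrow. None of these safeguards makes the sentence right. Nor does any of them make a woman renew the commitment, including the 28 days of contraception before starting, when she may have been off treatment for longer than the 12 weeks covered.

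**Conclusion.** The Section 7.2.1.2 sentence is wrong as written and should be corrected. The realistic consequence is an unneeded delay or an unneeded 25% reduction at a site that relies on that sentence alone. This assumes a literal reading of the section; a site working from Table 5 or Section 7.2 would act correctly. The size is one sentence against three, bearing on two rows of Table 5, with no derivable number of subjects or doses.

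This is an internal inconsistency. A reader might take it for a deliberate dosing choice, but the three opposing statements rule that out. The definition enters neither the error-rate control, nor the sample size, nor the primary analysis, so alpha, power and the primary result are unaffected.

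The re-entry gap is real but minor: one criterion, one sex, one exceptional group, with several safeguards still in place.

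**What to change.** 1. In Section 7.2.1.2, replace the condition of within 14 days by 14 days or more after transfusion, so that it matches footnote b of Table 5. This adds no procedure.
2. As a separate minor correction, list inclusion criteria 6, 7 and 8 in both Section 3.1.4 and Section 6.4. Extend the Section 6.4 check and Table 3, footnote 18, to luspatercept discontinuers re-treated open-label, so that women re-confirm criterion 7 before re-dosing. This adds one eligibility confirmation for that group.

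Both can be made by clarification letter or in the next amendment.

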**Table 5: Dose Delay, Dose Reduction and Discontinuation Guidelines:**

Event at the Day of Dosing	Action
Any related AE = Grade 2 a	Dose delay c until resolved to $\leq$ Grade 1 or baseline
Any related AE $\geq$ Grade 3 a	Dose delay c until resolved to $\leq$ Grade 1 or baseline, and then reduce dose by 25% d

**Table 5: Dose Delay, Dose Reduction and Discontinuation Guidelines: (Continued)**

Event at the Day of Dosing	Action
> 2 dose reductions due to related AE a	Discontinue treatment
Increase in Hb >2.0 g/dL compared to pre-dose Hb of Day 1 of the previous treatment dose cycle b	Reduce dose by 25% d if ΔHb not influenced by RBC transfusions
Hb ≥ 11.5 g/dL b	Dose delay until Hb ≤ 11.0 g/dL
Worsening of Anemia	

A ≥ 50 % increase from baseline in transfusion burden in combination with an unexplained shift from baseline (worsening) of ≥ 2 gradesi in leukopenia, neutropenia or thrombocytopeniah.
	
Dose delayc and repeat WBC, neutrophils and platelets weekly for two consecutive weeks.
 
 
• If WBC, neutrophils and platelets are resolved to ≤ Grade 1 or baseline, continue with dosing at the same dose level.
 
• If WBC, neutrophils and platelets are Grade 2 and above baseline, then continue with dose delay until resolution to ≤ Grade 1 and evaluate for alternative explanations of cytopenia as per standard clinical practice.
 
• If shift (worsening) of ≥ 2 grades is maintained for ≥ 14 days or thrombocytopenia does not improve to < Grade 2 within 14 days and no alternative explanation is identified, then perform bone marrow assessment.                         
 
○ If hematologic malignancy is confirmed, discontinue treatmentg
 
○ If hematologic malignancy is not confirmed, then discuss future dosing with medical monitor.
 
 
 

WBC	

WBC counte ≥2X baseline in the absence of an associated condition (eg, infection or concomitant corticosteroid use)
	
Continue treatment, repeat WBC within 1 week
 
 
• If repeat WBC remains ≥ 2 X above baseline Investigator should assess the cause of increase to exclude hematologic malignancy as per standard clinical practice.
 
• If hematologic malignancy is confirmed, discontinue treatment.g
 


WBC counte ≥ 3X baseline
	
Dose delayc with weekly WBC monitoring until WBC count <3 X baseline.
 
 
• Investigator should assess the cause of increase per standard clinical practice to exclude hematologic malignancy.
 
• If hematologic malignancy is confirmed, discontinue treatment.g
 

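### For a haemoglobin rise above 2.0 g/dL that is not due to transfusion, Protocol Section 7.2 can be read as withholding the dose while Table 5 orders a reduced dose without delay.

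*Protocol*

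**What the plan says.** Protocol Section 7.2 introduces a list with "The investigational product should be administered according to the following criteria". The first item requires a pre-treatment or pre-transfusion Hb below 11.5 g/dL, together with a rise of at most 2.0 g/dL "compared to the pre-dose Hb of Day 1 of the previous treatment dose cycle". The section then points to Table 5 "for guidelines on dose modifications and dose delays".

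Table 5 is organised by events on the day of dosing. Its Hb-rise row is triggered by "Increase in Hb >2.0 g/dL compared to pre-dose Hb of Day 1 of the previous treatment dose cycle". The action is "Reduce dose by 25" per cent, "if ΔHb not influenced by RBC transfusions". No delay is written in that row. The next row, for Hb of 11.5 g/dL or more, reads "Dose delay until Hb ≤ 11.0 g/dL".

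Section 7.2.1.2 says that Hb not influenced by transfusion is to be used for dosing actions, and describes it as a value taken within 14 days after a transfusion. Footnote b to Table 5, attached to both Hb rows, describes it as a value taken 14 days or more after a transfusion.

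SAP Section 9.4 tabulates delays and reductions separately, with reasons. For delay, the only Hb reason it names is a level of 11.5 g/dL or more, alongside a residual category of other reasons. For reduction, it names increased or high Hb.

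**The concern.** The two texts share one cut-off and one comparator, so any subject who meets the Table 5 trigger has failed a Section 7.2 condition. Read literally, Section 7.2 means no dose that day, while Table 5 means a smaller dose that day. Protocol Section 1.2.1.4 names excessive or rapid Hb increases as a risk and relies on the dose rules to limit it, so the rule should have one meaning.

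The two readings also lead to different places. A withheld dose counts towards the 15-week limit after which treatment stops (Section 7.2.1.2). A reduction moves the subject down the dose ladder in Table 4. In the exposure tables the same finding can appear as a delay for other reasons or as a reduction for Hb.

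**Working it through.** No sample size, power or error rate enters this point, so the check compares the texts.

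**1. Are the two conditions complements?** Section 7.2 requires a rise ≤ 2.0 g/dL; Table 5 acts on a rise > 2.0 g/dL. Both measure from the pre-dose Hb of Day 1 of the previous cycle. They are exact complements, with no gap and no overlap.

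**2. What does Table 5 order when each Section 7.2 criterion fails?**

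| Section 7.2 criterion | Event when it fails | Table 5 action |
|---|---|---|
| Hb < 11.5 g/dL | Hb ≥ 11.5 g/dL | Delay until ≤ 11.0 g/dL |
| Hb rise ≤ 2.0 g/dL | Rise > 2.0 g/dL | Reduce by 25% if not transfusion-influenced; no delay |
| Related AE below Grade 2 | Grade 2, or Grade 3 and above | Delay; at Grade 3 and above, delay and then reduce by 25% |
| WBC < 3 × baseline | ≥ 3 × baseline | Delay |
| Cytopenias below Grade 3 | Grade 3 or above | Delay |
| Limits on combined transfusion-burden increase and cytopenia shift | ≥ 50% increase with ≥ 2-grade shift | Delay |

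Five of the six pair with a delay, which agrees with not dosing that day. The Hb-rise row is the one exception. The Grade 3 AE row shows that Table 5 states both steps when it intends a delay followed by a reduction.

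**3. Does the protocol use Section 7.2 as a gate?** Yes, in two places. Table 3 footnote 3 has Hb checked before dosing so that it falls in the range Section 7.2 allows, and also so that Table 5 is followed; the two apply together. Sections 6.2.1 and 6.3.1 continue an Hb-related delay until the Section 7.2 administration criteria or the discontinuation criteria are met. (For the Open-label Phase, Section 6.4.1 refers to Sections 7.2.1.2, 7.2.1.3 and 11.1 instead.) No passage says that Table 5 overrides Section 7.2.

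**4. Is a delay implied for this row?** The signals are mixed. Footnote b, attached to the row, asks for weekly Hb checks during a delay, and Section 7.2.1.2 mentions a delay due to Hb increase. Yet the row orders none and gives no level at which dosing would resume.

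**5. When do the texts collide on their own?** If another criterion also fails, Table 5 delays for that reason. The clean conflict needs current Hb < 11.5 g/dL and a rise > 2.0 g/dL, so the previous pre-dose Hb must have been below 11.5 − 2.0 = 9.5 g/dL. The documents do not say how often this happens.

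**6. Is uninfluenced Hb defined once?** No. Sections 6 and 7.2 and Table 5 footnote b use 14 days or more after transfusion; Section 7.2.1.2 uses within 14 days. The Table 5 action depends on this definition.

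**The case against.** The strongest reply is that the texts can be read together. Section 7.2 would cover an unchanged dose, and its references to Table 5 would hand over to the table whenever a criterion fails. Section 7.2.1.2 describes reductions for Hb change as detailed in Table 5, and SAP Section 9.4 treats increased Hb as a reason for reduction. Reading Section 7.2 as an absolute bar would leave the Hb-rise row with nothing to do on the dosing day. The justification for an earlier amendment also records that the rise wording in Section 7.2 was edited for consistency with Table 5.

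This reading is plausible, and may be what the sponsor meant. But it needs words that Section 7.2 lacks, and it sits badly with the use of Section 7.2 as a gate. The edit recorded in the amendment aligned the comparator and left the differing actions in place.

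Two stronger readings might tempt a reader. The first is that for a transfusion-influenced rise Table 5 asks for nothing while Section 7.2 still withholds, so that a full dose becomes a third possible outcome. The documents do not support this: Sections 6, 7.2 and 7.2.1.2 and footnote b all direct that pre-transfusion or uninfluenced Hb be used for dosing. The second is that the exposure tables become non-comparable across sites. SAP Section 9.4 plans these tables by treatment group and total, so no planned output compares sites.

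**Conclusion.** For a rise above 2.0 g/dL that is not influenced by transfusion, the protocol supports two actions, withholding or reducing, and does not rank them. The contradictory 14-day definition adds doubt about which values the row covers. This should be corrected, but it is limited in reach. It concerns dosing safety for a named risk, and whether an event is coded as a delay or a reduction within pooled by-arm counts. Because Hb increase is an expected drug effect, affected visits should fall mainly in the luspatercept arm.

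The primary and key secondary tests are computed from transfusion records in all randomised subjects, and neither they nor the sample size depend on this rule. The frequency is not given. Dose changes pass through the interactive response system and the sponsor is notified within 24 hours, so practice may have been more uniform than the text; the documents do not show whether it was. The conclusion rests on the wording alone and takes no position on which action is right.

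**What to change.** Reconcile Section 7.2, Section 7.2.1.2 and the Table 5 Hb-rise row with footnote b, so that they state one action for an uninfluenced rise above 2.0 g/dL and one definition of uninfluenced Hb. If Table 5 is meant to govern when a Section 7.2 criterion fails, say so in Section 7.2. If a delay is meant, the row should say so and state when dosing resumes. The choice is a clinical decision for the sponsor.

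Then align the delay and reduction reasons in SAP Section 9.4 with that rule. For data already recorded, show doses withheld for a rise above 2.0 g/dL under their own reason instead of under other reasons, where the recorded reason allows it.

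The cost is a wording correction, a clarification to sites and one added reason in descriptive tables. No efficacy analysis changes.
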